#### **4.4.2.3 Reporting of serious adverse events**

##### **Investigator reporting**

When the investigator becomes aware of a SAE during the course of the study, the SAE must be reported to the local monitor or other AstraZeneca/Contract Research Organization representative within one (1) day and a completed written SAE report must be sent within four (4) calendar days. Follow-up information should be reported by the investigator within one (1) day and in writing within four (4) calendar days.

All SAEs have to be reported, whether or not considered causally related to the investigational product. All SAEs will be recorded in the case report form. The investigator is responsible for informing the Ethics Committee and/or the Regulatory Authority of the SAE as per local requirements.

#### **4.4.3 Laboratory safety measurements and variables**

##### **4.4.3.1 Methods of assessment**

A laboratory screen, which includes haematology, clinical chemistry and urine analysis will be performed. A laboratory screen will also be done in case of premature discontinuation from the study. The visit 3 laboratory screen, or visit 1 for untreated subjects, is to be regarded as baseline data. The subjects should be fasting at least 12 hours before sampling.

The laboratory variables are

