### Run-in period

The study will start with a 12-week run-in period. Subjects will have either been treated or untreated with a PPI prior to entering this phase of the study. The subjects will receive both oral and written subject information and sign a consent form. At visit 1 all subjects will undergo a physical examination, including vital signs and demographics. Medical and surgical history, especially for GERD will be recorded.

All subjects will attend an "Investigational week". This "week" will allow the collection of baseline data, such as endoscopy with biopsy sampling, 24-hour pH metry, manometry, SAP and laboratory measurements. A 24-hour pH metry performed within 12 months prior to enrolment could be accepted, if made according to the method stated i.e. no antisecretory medication 7 days prior to investigation. Manometry will only be performed at the first occasion of pH metry in all subjects.

The "investigational week" can take place either immediately or 6 weeks after treatment with esomeprazole 40 mg o.d. depending on:

- Whether the subject was treated or untreated with PPI prior to enrolment
- Whether the clinic can offer 24 hr pH metry and SAP within 2 weeks from visit 1 for the untreated subjects.

Esomeprazole must be withheld at least 7 days (visit 2) prior to the "Investigational week".

Dose adjustments are not allowed during the run-in period.

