### **3.4.5 Pre-study, concomitant and post-study treatment(s)**

Subjects entering this study have most likely been on long-term treatment with various anti-acid secretion therapy (i.e. PPI, H2RA). During the 12 week run-in period the subject must undergo the “Investigational week” including endoscopy with biopsy sampling, 24 hr pH-metry, manometry, SAP and laboratory measurements. In order to get relevant pH measurements the study medication (esomeprazole 40 mg o.d.) must be stopped at least 7 consecutive days before the 24 hr pH-metry at visit 3. Subjects randomized to anti-reflux surgery should be treated with

esomeprazole (20 mg o.d. to 40 mg daily) before surgery (within three months from randomization).

Motility activators (prokinetic drugs) e.g. metoclopramide are allowed for operated subjects between visit 5 and visit 6 for treatment of post-operative intestinal paralysis.

In case of an ulceration/erosion in the fundoplication within 3 months post surgery, subjects are allowed to be treated with esomeprazole 40 mg o.d. for 2-12 weeks. Subjects in the surgical arm are instructed to take antacid/alginate medication if they experience dyspeptic symptoms after surgery. If the subject has need for additional medication he/she shall contact the investigator who may dispense 1 bottle of esomeprazole 20 mg to be taken on demand, not more than one tablet daily. Unused medication is to be returned on the following visit (visit 7) and drug accountability is to be recorded in the CRF. After visit 7 no such medication is allowed. Subjects in the surgical arm, who develop a gastric or duodenal ulcer due to intermittent usage of NSAID are allowed to be treated with esomeprazole 40 mg o.d. for 2 weeks.

Concerning *Hp* eradication please see Section 3.1.

Antacids and alginates are allowed during the study.

Other medication which is considered necessary for the subject's safety and well being may be given at the discretion of the investigator(s). The administration of all medication (including investigational products, antacids and alginates) must be recorded in the appropriate sections of the case report form (CRF).

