**Table 4 Safety objectives and endpoints relating to each objective**

Objective	Endpoints	Summary statistic for analysis (including timepoint and population)	Planned analysis	Significance of results
4.4.3 Laboratory screen variables	Laboratory assessments	
 
- Descriptive presentation of laboratory results for each sample occasion.
 
- Number of subjects with values below, within and above the reference range, over time.
 
- Median changes between baseline and the last visit for each laboratory variable.
 
- Graphs showing last visit values versus the baseline values for each laboratory variable.
 
-All clinical laboratory presentations will be made for the safety population.
 
	No formal statistical comparison.	The result will contribute to the determination of the adverse drug reaction pattern and frequency during long-term treatment with esomeprazole.
4.4.2 SAE and AE	Occurrence and nature (seriousness intensity and action taken to study drug due to AE) of all SAEs and AEs causing premature discontinuation of study drug and /or study.	
 
-Frequency of subjects with SAEs and AEs leading to discontinuation of study drug and/or study.
 
-AE pattern (e.g. by system organ classification)
 
- SAEs and discontinuations due to AE will be presented for the safety population
 
	No formal statistical comparison.	The result will contribute to the determination of the adverse drug reaction pattern and frequency during long-term treatment with esomeprazole.

The methods for collecting safety data are described below

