### **6.2.3 Statistical analyses**

The two treatment groups will be compared regarding the primary endpoint using Life Table methods for graphic presentation and a log rank test (two-sided) for statistical inference. In both the ITT and the PP analyses data will be censored in case of discontinuation due to reasons other than treatment failure. Post-operative complications, histopathology, endoscopy and symptoms are summarized using frequency tables.

For subjects randomized to the surgery group, post-operative complications during the first month after surgery will be assessed descriptively. Quantitative data on post-operative complications will be tabulated with Mean, SD, min and max. For post-operative complications data with nominal or ordinal outcome, the number of subjects and relative frequency distribution will be presented.

Histopathological changes will be assessed by frequency tabulation by treatment group and visit.

The number of endoscopic and/or symptomatic relapses at clinical visits will be presented by visit and treatment group with frequency tables. Mean, SD, min and max, both combined and separately.

Number of endoscopic and/or symptomatic relapses between visits will be presented by time period (subject year) and treatment group with frequency tables. Mean, SD, min and max, both combined and separately.

GI symptoms associated with GERD over time will be presented by visit and treatment in frequency tables and as number and proportion of subjects with no symptoms.

The percentage of 24 hr intragastric pH  $\leq 4$  will be presented using descriptive methods (Mean, SD) by visit and treatment group.

Symptom Association Probability (SAP) will be presented using descriptive methods (Mean, SD) by visit and treatment group.

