### Safety analyses

The laboratory data will be presented in terms of median, Mean and SD for the baseline value, the last visit value and the change from baseline to last visit. A cross-table showing the number of subjects with the values below, within and above the normal range at baseline versus the same classification at the last visit will be provided for each laboratory variable. Graphs showing last visit values versus the baseline values and descriptive presentation over time will be presented for each treatment group and each laboratory variable.

Serious adverse events and AEs causing premature discontinuation of study drug and/or study will be presented descriptively.

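### The laboratory baseline combines samples taken before any study drug with samples taken after about 6 weeks of esomeprazole 40 mg and a short washout, so pooled within-arm change and shift tables can mislead if drug effect carries over

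*Protocol*

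**What the plan says.** Protocol Section 4.4.3.1 sets one baseline rule for the laboratory screen: "The visit 3 laboratory screen, or visit 1 for untreated subjects, is to be regarded as baseline data".

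Section 3.1 (Run-in period) explains how the two visits differ. The week of baseline investigations "can take place either immediately or 6 weeks after treatment with esomeprazole 40 mg o.d", depending on whether the subject was on a PPI before enrolment and on how soon pH-metry can be arranged. Before it, "Esomeprazole must be withheld at least 7 days (visit 2) prior to the" investigations. Section 3.4.5 repeats that esomeprazole "must be stopped at least 7 consecutive days before the 24 hr pH-metry at visit 3" and gives one reason, namely to make the pH measurements relevant. The same section describes the population: "Subjects entering this study have most likely been on long-term treatment with various anti-acid secretion therapy".

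The Safety analyses part of Section 6.2.3 summarises laboratory data as "the baseline value, the last visit value and the change from baseline to last visit". It adds a cross-table of below, within and above range at baseline against last visit. Table 4 plans median changes from baseline with no formal comparison, and says the result contributes to "determination of the adverse drug reaction pattern and frequency during long-term treatment with esomeprazole". Neither place separates visit 1 baselines from visit 3 baselines. Histology is handled differently: "Histopathological changes will be assessed by frequency tabulation by treatment group and visit".

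**The concern.** One baseline label covers two exposure states. Section 4.4 says the study is designed to look at changes in laboratory variables, and it names gastrin, chromogranin A, vitamin B12 and homocysteine. Nothing in the protocol says that 7 days off drug returns these to their untreated level. That interval was chosen for pH recording.

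If some drug effect is still present at visit 3, two things follow for subjects with a visit 3 baseline:

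- **Medical arm:** a value already shifted at baseline that stays shifted under continued treatment counts as no change, and sits on the diagonal of the shift table. The drug's effect looks smaller than it is.
- **Surgical arm:** the residual effect fades once esomeprazole stops, and appears as a laboratory change after the operation.

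At stake is how the descriptive laboratory results are read. The primary efficacy comparison is not affected.

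**Working it through.** **Which visit supplies the baseline**

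| Subject | Laboratory screen under Section 3.1 and Table 1 (footnotes 5 and 9) | Baseline under Section 4.4.3.1 |
|---|---|---|
| On PPI before the study | Visit 3, on the esomeprazole 40 mg route | Visit 3 |
| Not on PPI, pH-metry within 2 weeks of visit 1 | Visit 1, before study drug | Visit 1 |
| Not on PPI, pH-metry later than that | Visit 3, after esomeprazole from visit 1 | Visit 1, where no screen was taken |

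The third row is a contradiction. Read literally, Section 4.4.3.1 gives these subjects a baseline that the schedule does not collect. It also means that prior PPI status alone does not separate the two exposure states.

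**Timing (Table 1)**

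Visit 1 is at week -12, visit 2 at week -6 (±1 week) and visit 3 at week -5.

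- Exposure before visit 2: 12 - 6 = 6 weeks, with a range of 12 - 7 = 5 to 12 - 5 = 7.
- Off drug before visit 3: 6 - 5 = 1 week nominal. The consent list in Section 8.3 speaks of two weeks without treatment, which may include the investigational week. The time off drug at sampling is therefore at least 7 days.

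**Effect on mean change**

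The protocol gives no figure for this point, so there is none to reproduce. Define:

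- full long-term effect of esomeprazole on a variable = 1 unit;
- q = share of subjects with a visit 3 baseline. It is not given; the assumed range is 0.3 to 1.0;
- r = share of that effect still present at visit 3. It is not given; the assumed range is 0 (complete washout) to 1.

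Assume also that visit 1 samples carry no effect, that medical subjects show the full effect at last visit, and that surgical subjects show none. Randomisation gives both arms the same expected q and r. Then:

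- mean baseline in either arm = q·r
- medical change = 1 - q·r
- surgical change = 0 - q·r
- difference = (1 - q·r) - (-q·r) = 1

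| q | r | Medical change | Surgical change | Difference |
|---|---|---|---|---|
| any | 0 | 1.00 | 0.00 | 1.00 |
| 0.3 | 0.25 | 0.925 | -0.075 | 1.00 |
| 0.3 | 0.5 | 0.85 | -0.15 | 1.00 |
| 0.7 | 0.25 | 0.825 | -0.175 | 1.00 |
| 0.7 | 0.5 | 0.65 | -0.35 | 1.00 |
| 0.9 | 0.5 | 0.55 | -0.45 | 1.00 |
| 0.7 | 1 | 0.30 | -0.70 | 1.00 |

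For example, q = 0.7 and r = 0.5 give q·r = 0.35. Medical change is then 1 - 0.35 = 0.65, surgical change is -0.35, and the difference is 0.65 + 0.35 = 1.00.

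The rows with r = 1 are bounds. They require the whole long-term effect to be present by visit 3 and none of it to fade off drug. The identity is for means. Table 4 uses medians and category counts, for which the direction of the problem is the same but these figures do not carry over.

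**The case against.** The case against has several parts.

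**Pooling is inferred from silence.** No sentence orders the two baselines to be combined, and a statistical analysis plan, not shown here, may split the tables. That is fair, and nothing should be concluded about that plan. But the protocol itself fixes the baseline rule and the displays that depend on it, and the rule conflicts with the schedule whatever a later plan does.

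**Much of the remedy is already planned.** Table 4 and the safety analyses provide results by sampling occasion and over time for each arm, so medical and surgical values can be compared without any baseline. This stands, and it limits the harm. The change and shift tables still remain among the displays that are to inform on the drug's long-term reaction pattern.

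**The randomised contrast is sound.** This also stands. Both arms share the run-in, so the mix balances in expectation.

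**The size is assumed.** This stands too. The statement in Section 3.4.5 on earlier therapy covers H2 blockers as well as PPIs, while the run-in route depends on PPI use, so it does not supply q. Nothing supplies r.

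**A reader might infer more than the text supports:**

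- that visit 1 subjects are drug-naive. The protocol says only that they were untreated with PPI before the study, which does not exclude H2 blockers or earlier PPI courses;
- that biopsy change from baseline is distorted in the same way. Section 4.4.3.1 covers the laboratory screen only, and histology is tabulated by group and visit with no planned change from baseline.

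**Conclusion.** The point holds in a conditional form, for laboratory data only. The baseline rule mixes samples taken before study drug with samples taken after about 6 weeks of esomeprazole 40 mg and at least 7 days off it. The planned change and shift tables do not distinguish them. Under the stated assumptions, mean within-arm change moves by -q·r in both arms: zero if washout is complete, and 0.35 of the drug effect at q = 0.7 and r = 0.5. The carry-over may differ between variables.

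It would be tempting to say that the plan understates esomeprazole's long-term effects and shows false changes after surgery. The documents do not support that as a fact, because they give neither the share with a visit 3 baseline nor the carry-over. Nor do they support a claim that the comparison between arms is biased by the baseline mix, since that shift is zero for every q and r.

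Separately, and without any assumption, Section 4.4.3.1 contradicts Section 3.1 and Table 1 for untreated subjects whose pH-metry is delayed.

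**What to change.** 1. Reconcile Section 4.4.3.1 with Section 3.1 and Table 1 (footnotes 5 and 9). Define baseline by the visit at which the run-in screen was actually taken, so that untreated subjects with delayed pH-metry are covered.
2. In Table 4 and the safety analyses, show laboratory change and shift tables by baseline visit and by prior PPI status. Prior PPI status alone is not enough, because some untreated subjects have a visit 3 baseline.
3. Base statements about esomeprazole's laboratory effects on the medical-versus-surgical difference at the scheduled laboratory visits (8, 12, 16, 33 and 39). Treat pooled within-arm change as supportive.
4. For histology, add only a note that the baseline row mixes visit 1 and visit 3 biopsies.

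The cost is wording, programming and more tables. Prior PPI status and the route through run-in already have to be known to schedule the visits. The visit 1 stratum may be small. With 275 subjects per arm it would be about 0.3 × 275 = 83 per arm if q = 0.7, and about 0.1 × 275 = 28 if q = 0.9, before attrition. It should therefore serve as a check on the pooled tables and not as the sole basis for a conclusion.

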##### Haematology

Haemoglobin, MCV, leukocytes, thrombocytes

##### Clinical chemistry

Creatinine, ASAT, ALAT, Alk. Phosphatase, total bilirubin, Sodium, Potassium, TIBC, s-Fe, ferritin, triglycerides, b-ery-folate, Cholesterol (LDL, HDL, LDL/HDL), Zinc, Calcium (albumin corr), D-vitamins, Gastrin, Chromogranin A, Homocysteine, Vitamin B12

## Urine analysis

Protein, glucose, WBC, RBC

Haematology, clinical chemistry and urine will be analysed by a central laboratory. An accredited central laboratory will be chosen for sample collection, labelling, storage and shipment. This information will become available at a later date. Instructions for sampling, preparation of samples, request forms, labels and materials for collection and shipping of samples will be provided by the central laboratory.

### **4.4.3.2 Calculation or derivation of endpoints**

Not applicable

## **4.5 Quality of Life measurements and endpoints**

### **4.5.1 Summary of Quality of Life objectives and endpoints**

Table 5 shows how the Quality of Life endpoints of this study relate to the study objectives.

**Table 5 Quality of Life objectives and endpoints relating to each objective**

Objective	Endpoint(s)	Summary statistic for analysis (including timepoint and population)	Planned analysis	Significance of results
Patient reported outcomes (PRO)	GSRS and QoLRAD questionnaires at clinical visits	Mean change from baseline for each prespecified dimension ITT population	Descriptive, for treatment comparisons baseline assessment will be used as covariate	

The methods for collecting Quality of Life data are presented below

### **4.5.2 Patient reported outcomes**

Symptoms of heartburn and acid regurgitation impact the everyday life of subjects and consequently their Health Related Quality of Life (HRQL). HRQL is a subjective multidimensional concept used to measure treatment efficacy. Hence, HRQL has become a significant endpoint when evaluating the effectiveness of treatments in clinical trials, in particular for conditions that lack objective markers of disease activity. For these conditions, adequate symptom control may best be defined as sustained reduction of symptoms to a level that does not cause significant impairment in HRQL (Dent J et al 1999).

#### 4.5.2.1 Methods of assessment

The evaluation of patient-based outcomes in this study focuses on reflux symptoms and the impact thereof on subjects' daily life. Therefore, a symptom questionnaire, the Gastrointestinal Symptom Rating Scale (GSRS), will be used together with a disease-specific HRQL-questionnaire, the Quality Of Life in Reflux And Dyspepsia (QOLRAD), which was specifically developed for subjects with symptoms of reflux and dyspepsia. GSRS

The GSRS covers 15 GI symptoms and uses a 7-graded Likert scale to rate each symptom. The GSRS contains five dimensions depicting Indigestion (item no 6, 7, 8, 9), Diarrhoea (item no 11, 12, 14), Constipation (item no 10, 13, 15), Abdominal pain (item no 1, 4, 5) and Reflux (item no 2, 3). In the GSRS, the lower the value, the less are the perceived GI symptoms, (Appendix I). The reliability and validity of the GSRS have previously been documented ([Revicki DA et al 1998](#)) and there are norm values available for a healthy population ([Dimenäs E et al 1996](#)). The GSRS has previously been used to assess symptom relief during treatment with omeprazole in subjects with GERD ([Havelund T et al 1999](#)).

#### QOLRAD

The impact of heartburn and acid regurgitation will be assessed using the QOLRAD questionnaire (Appendix J). The questionnaire consists of 25 items combined into the dimensions Emotional distress (item no 12, 14, 15, 17, 19, 22), Sleep dysfunction (item no 8, 10, 11, 18, 21), Vitality (item no 1, 4, 7), Food/drink problems (item no 3, 5, 9, 13, 16, 20) and Physical/social functioning (item no 2, 6, 23, 24, 25). The questions are rated on a 7-graded Likert scale, the lower the value, the more severe is the impact on the daily functioning. The QOLRAD has been extensively documented in international studies in subjects with heartburn with regards to reliability ([Pickard AS et al 2004](#)), validity ([Wiklund IK et al 1998](#)) and responsiveness ([Talley NJ et al 2001](#)). Previous studies have revealed that a change of 0.5 represents a minimum important change in the QOLRAD ([Wiklund IK et al 2000](#)).

The translations of the questionnaires into other languages have been done according to proposed guidelines involving several independent translators.

Based on previous studies, the Reflux and the Indigestion dimension in the GSRS questionnaire have been selected as treatment outcomes. In the QOLRAD a beneficial impact on symptom relief is expected in terms of the Sleep and Food /Drink dimensions. Subjects with GERD have previously reported acid-related sleep disturbances. For the prespecified dimensions, the mean change from baseline to end of the study will be assessed.

The questionnaires are self-administered and the subject will be asked to complete the questionnaires at Visit 4, 8, 10, 12, 14, 16, 31, 33, 35, 37 and 39 and in case of early discontinuation from the study.

Appropriate procedures for minimizing bias and enhancing compliance will be followed throughout the study. To ensure this, a study co-ordinator at each site will be responsible for the PRO evaluation and a standardized procedure for the administration of the questionnaires

will be applied. The subject will complete the questionnaires independently. Each site will have a designated quiet space in the clinic for subjects to complete the questionnaire at each appropriate visit. The questionnaires will be completed **prior** to other examinations, before there are substantial professional encounters with transmission of information, such as disease status. Such information may influence the answers that subjects provide on questionnaires.

A manual describing the HRQL questionnaires and instruction manuals on the standardized administration and other practical issues will be provided to all involved study personnel. The manual will include guidelines for handling issues that can arise with the PRO assessment, including answers to questions that are commonly asked. Careful training will be given to study personnel to ensure the data quality through the standardised administration of the questionnaires. Group training sessions for all involved will be held at each site. In addition, clinical study monitors will be trained to evaluate the quality of the PRO assessments and alert sites to possible problems in this component of the trial.

